11.7 Coagulopathy

Values for the following coagulopathy panel and change from Baseline values will be summarized through descriptive statistics by treatment group and visit.

Additionally for D-Dimer, the percentage change from Baseline values will also be summarized by treatment group and visit. The mean change and mean percentage change from Baseline up to Day 14, using the actual study day for Day14/EOT assessments, will be plotted per treatment group using line graphs. A non-parametric Wilcoxon Rank Sum test will be used to compare

the treatment groups with respect to the percentage change from baseline values at Day 7 and Day 14/EOT.

- D-dimer
- Fibrinogen
- Platelet count
- Prothrombin time (PT)
- Partial thromboplastin time (PTT)
- International normalized ratio (INR)

A separate summary table will be produced, similar to what is described above, summarizing the results at Day 7 (assessments taking place on study day 7), Day 14 (assessments taking place on study day 14) and Day 28 (assessments taking place on study day 28). For any patients with missing Day 7 results, the Day 7 results will be imputed using the last value reported prior to study day 7. Similarly, Day 14 missing observations will be imputed with the last available assessment that took place after study day 7 and prior to study day 14. Day 28 missing observations will be imputed with the last available assessment that took place after study day 14. A summary table will be produced, summarizing these (imputed and reported) results. This data will also be presented using a boxplot.

11.7.1 Time to first time back to normal

Time to first time back to normal (in days) is the number of days between the date of first study drug administration and the first date that the result of a coagulopathy parameter returns back to within a normal range.

Time to first time back to normal will be analyzed using a Cox proportional hazards model to estimate the hazard ratio and corresponding 95% CI for SIR1-365 dose vs placebo.

The proportional hazard regression model will include a single term for treatment.

- Patients with a baseline value falling within the normal range will be censored on the first date of study drug administration.
- Death prior to returning back to normal will be handled as a competing risk event.
- Patients that do not return back to normal over the assessment period will be censored at the date of last assessment
- Patients with no post-baseline assessment value will be censored at Day 1.

The hazard ratio estimation of the event of interest (first time back to normal) will be derived from a cumulative incidence function. The Kaplan Meier estimate of median time to event will also be presented for each treatment group.

11.8 Cardiac Function Damage

Cardiac function damage panel including NT-proBNP (or BNP) and high sensitivity cardiac troponin will be summarized using descriptive statistics at Baseline and at each post-baseline time point by treatment group. Changes from Baseline will also be summarized.

A separate summary table will be produced, similar to what is described above, summarizing the results at Day 7 (assessments taking place on study day 7), Day 14 (assessments taking place on study day 14) and Day 28 (assessments taking place on study day 28). For any patients with missing Day 7 results, the Day 7 results will be imputed using the last value reported prior to study day 7. Similarly, Day 14 missing observations will be imputed with the last available assessment that took place after study day 7 and prior to study day 14. Day 28 missing observations will be imputed with the last available assessment that took place after study day 14. A summary table will be produced, summarizing these (imputed and reported) results.

11.9 Correlation Analysis for Safety Outcomes

Correlation of biomarker levels to safety outcomes will be assessed between the proportions of safety outcomes, i.e TEAE and SAE with Baseline levels of inflammatory biomarkers using logistic regression analysis as detailed below.

A logistic regression model will be fitted to the binomial presence (Yes/No) of adverse events per patient as a function of treatment, Baseline biomarker and the interaction between treatment and Baseline biomarker as fixed effects.

The regression coefficients, 95% CI and corresponding P-values will be reported and used to assess the association between the following Baseline biomarker parameters and the proportion of TEAE and SAE per treatment group:

- Baseline CRP
- Baseline Ferritin and lymphocyte counts

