6 DETERMINATION OF SAMPLE SIZE

Due to the exploratory nature of this study, the sample size is not calculated based on statistical significance on any parameters. However, a sample size of 30 patients per group is considered to be sufficient to detect marked differences in the overall safety profile between treatments with a pre-specified safety monitoring plan. Furthermore, this sample size provides estimates of treatment differences in some clinical efficacy endpoints and the levels of some biomarkers such as CRP, for use in planning future studies. Therefore, approximately 30 patients will be enrolled for each group (total 60) in this study.

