7 RANDOMIZATION

Patients will be randomized to one of the 2 treatment groups: SIR1-365 100 mg or placebo at a 1:1 ratio. Randomization will be stratified according to age group (2 levels: < 60 or \geq 60 years), Dexamethasone use (2 levels: Yes or No), and Remdesivir use (2 levels: Yes or No).

Randomization will be controlled by a web-based Randomization and Trial Supply Management (RTSM) system.

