8 GENERAL ANALYSIS CONSIDERATIONS

The statistical analyses will be reported using summary tables, listings, and figures (TLFs). The International Council for Harmonisation (ICH) numbering convention will be used for all TLFs.

Unless otherwise noted, all statistical testing will be 2-sided and will be performed at the 0.05 significance level. Tests will be declared statistically significant if the calculated P-value is <0.05 .

Continuous variables will be summarized by presenting the number of observations, mean, standard deviation, median, minimum, and maximum. Other summaries (eg, 95% confidence interval [CI]) may be used as appropriate.

Categorical variables will be summarized by presenting counts and percentages of patients in corresponding categories. All possible categories as defined in the CRF should be populated, even

if they have zero counts. Percentages for missing values are omitted and do not account for the percent calculation of other categories. Percentages are based on the total category count excluding the missing category if not otherwise mentioned. In certain tables (eg, AEs), the total number of patients in the analysis set is used as denominator. Footnotes in the table will specify the percent basis in those cases.

All summary tables will be presented by treatment group and a total column (except efficacy tables). Baseline summaries will also include a total summary column.

Individual patient data obtained from the eCRFs, external vendors (eg, laboratory data, ECG data), PK data, and any derived data will be presented by patient in data listings.

The analyses described in this plan are considered a priori, in that they have been defined before breaking the blind.

Any analyses performed after breaking the blind which are not specified in this analysis plan (or subsequent version prior to unblinding) will be considered post hoc and exploratory. Post hoc analyses will be labeled as such on the output and identified in the CSR.

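### SAP 11.9 fits treatment-by-biomarker logistic models in about 60 patients with no provision for sparse outcomes; Firth's penalised likelihood should be specified

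*SAP*

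**What the plan says.** SAP 11.9 (Correlation Analysis for Safety Outcomes) is the planned analysis for a listed secondary safety measure: how safety outcomes vary with baseline inflammatory biomarkers. Its model is: "A logistic regression model will be fitted to the binomial presence (Yes/No) of adverse events per patient as a function of treatment", together with "Baseline biomarker and the interaction between treatment and Baseline biomarker as fixed effects". The outcomes are TEAE and SAE. The biomarkers are CRP and, on one line, "Baseline Ferritin and lymphocyte counts". On use of the results it says: "The regression coefficients, 95% CI and corresponding P-values will be reported and used to assess the association".

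SAP 6 gives the size: "approximately 30 patients will be enrolled for each group (total 60) in this study". It also says that "the sample size is not calculated based on statistical significance on any parameters". SAP 7 sets 1:1 allocation.

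SAP 11.9 names no estimation method. It has no separation check, no minimum number of events, no exact or penalised alternative, and no rule for dropping the interaction. Protocol 8.2 and 10.3.2 leave the details of this analysis to the SAP, so the gap is not filled elsewhere.

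**The concern.** With the interaction included, the model amounts to a separate intercept and slope in each 30-patient arm. What limits such a fit is the number of patients in the rarer outcome class. That class may be SAEs, if they are uncommon, or TEAE-free patients, if nearly everyone has a TEAE.

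If the class is empty in one arm, or if the biomarker splits the two outcomes perfectly within an arm, maximum likelihood has no finite solution for at least one coefficient. The software then prints an arbitrary large value with a meaningless Wald interval. If the data do not separate, the estimates are finite but carry small-sample bias and avoidable variance.

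The estimates and intervals from this analysis are meant to inform later studies. If a model fails, the analyst would have to choose a remedy after unblinding, and SAP 8 would label that choice post hoc.

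**Working it through.** **Inputs.** From the SAP: N of about 60, 30 per arm, 1:1 (SAP 6 and 7); three coefficients plus an intercept (SAP 11.9); two-sided 0.05 (SAP 8). Assumed, because the documents give none: the outcome rate (5% to 95%), the biomarker distribution and the true slopes. The plan has no figure of its own to reproduce here.

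**1. Rarer outcomes per coefficient** = 60 × rate / 3. At 10%: 60 × 0.10 / 3 = 2. At 20%: 4. At 25%: 5. At 50%: 10. A single joint ferritin-lymphocyte model with both interactions would have five coefficients, so at 10% only 6 / 5 = 1.2. SAP 11.9 does not say whether this is one model or two.

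**2. Probability that no finite estimate exists, with no biomarker effect (exact).** Within an arm of 30 with k events, the fit fails with probability 1 if k is 0 or 30, and otherwise with probability 2 / C(30, k), the chance that the events hold the k lowest or k highest biomarker values. Average over k ~ Binomial(30, p) to get s; over two arms the probability is 1 − (1 − s)².

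At p = 0.10:
- k = 0: 0.9^30 = 0.0424
- k = 1: 0.1413 × 2/30 = 0.0094
- k = 2: 0.2277 × 2/435 = 0.0010
- k ≥ 3: about 0.0001

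So s = 0.0530, and 1 − 0.9470² = 0.103.

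| Rate of rarer outcome | Expected number in 60 | P(no finite estimate) |
|---|---|---|
| 5% | 3 | 42% |
| 10% | 6 | 10% |
| 15% | 9 | 2.2% |
| 20% | 12 | 0.4% |
| 25% | 15 | 0.07% |
| 50% | 30 | about 0 |

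By symmetry the table also covers TEAE rates of 95%, 90% and so on. A true biomarker slope raises the risk somewhat: in simulation with a slope in one arm it was 44% to 48% at a 5% rate and 11% to 15% at 10%.

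**3. Bias and spread when estimates are finite (simulation).** Normal biomarker; slope 0 on placebo and 0.693 per SD on active, so the true interaction is 0.693. There were 2,000 maximum-likelihood (ML) runs per rate, summarised over non-separated datasets, and 600 Firth runs, separated datasets included.

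| Outcome rate | ML mean (median) | ML SD | Firth mean | Firth SD |
|---|---|---|---|---|
| 10% | 0.96 (0.79) | 1.93 | 0.71 | 0.98 |
| 15% | 0.90 (0.78) | 1.34 | 0.71 | 0.91 |
| 20% | 0.87 (0.80) | 1.17 | 0.71 | 0.78 |
| 30% | 0.85 (0.78) | 0.85 | 0.76 | 0.70 |
| 50% | 0.78 (0.74) | 0.69 | 0.68 | 0.59 |
| 80% | 0.87 (0.78) | 1.07 | 0.69 | 0.80 |
| 90% | 0.86 (0.75) | 1.86 | 0.60 | 1.08 |

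Mean inflation of the ML interaction runs from 0.78 / 0.693 = 1.13 at 50% to 0.96 / 0.693 = 1.39 at 10%.

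**4. Skewed biomarker** (log-normal, log-SD 0.7). The mean ML interaction is 1.31 at 10%, 1.02 at 20% and 0.86 at 50%. The direction is not uniform across coefficients: the active-arm slope averages 0.64 at 10% and 0.68 at 15%, close to or just below 0.693, but 1.64 at 90% (median 0.94).

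**5. Tests and precision.** With true slopes of zero, Wald rejection among finite fits was 0.1% to 4.1% for the slope and 0.1% to 5.6% for the interaction. It was lowest where one class was sparse. The median 95% CI half-width for the ML interaction in the normal-biomarker runs is 2.2 on the log-odds scale at a 10% rate and 1.22 at 50%. Even the latter is a factor of exp(1.22) = 3.4 either way.

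**The case against.** The case for leaving the section alone has four parts.

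- **No event rates.** Neither document gives a TEAE or SAE rate, so no one can say from them that outcomes will be sparse. Hospitalised patients with severe COVID-19 could have many SAEs, although Protocol Appendix 4 also narrows what counts as one. This stands, and every figure above is conditional on an assumed rate.
- **Separation is confined to the extremes.** A reader might infer that the plan will produce infinite estimates. The documents do not support that: from a 20% to an 80% rate the risk is negligible. This stands too.
- **No false positives shown.** A reader might infer that the models overstate the link between biomarkers and harm. For the tests this is not shown: null rejection is below or close to 5%. For the estimates, inflation is a feature of the mean. Medians move little, and with a skewed biomarker some slopes are not inflated at low rates. The greater risk to inference is missed associations and very wide intervals, and those come mainly from the sample size.
- **Limited consequence.** SAP 6 calls the study exploratory, and Protocol 10.3 says it is not powered for hypothesis testing and treats p-values as an aid to interpretation. That limits the importance of the point. It excuses wide intervals, but not the absence of a rule for a model that has no finite estimate.

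It is also true that the SAP does not name maximum likelihood. That is only the ordinary meaning of logistic regression with no method stated.

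**Conclusion.** The point holds as a gap in SAP 11.9: an interaction model in about 30 patients per arm with nothing said about sparse outcomes. With no biomarker effect, the chance of no finite estimate is about 10% if the rarer class is 10%, about 42% if it is 5%, and below 0.5% from 20% upwards. At rates between 10% and 90%, the finite maximum-likelihood interaction is biased away from zero by roughly 13% to 40% on average with a normal biomarker. Its SD is larger than Firth's at every rate tabulated, by a factor of about two at 10% (1.93 against 0.98).

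These sizes rest on assumed rates, slopes and biomarker distributions. They do not support saying that SAEs will probably be too few, that every coefficient is inflated, or that the tests give spurious associations. The matter is minor in rank, since the analysis is secondary and unpowered, but the improvement is real and cheap.

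**What to change.** In SAP 11.9, add: The logistic models, with the terms stated above, will be fitted by Firth's penalised likelihood, with profile penalised-likelihood 95% confidence intervals and penalised likelihood-ratio p-values.

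The same edit should say whether ferritin and lymphocyte count enter separate models or one joint model.

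The cost is a sentence in the SAP and a model option in the program, made before unblinding. The statistical downside is some over-shrinkage when one class is very rare. With a normal biomarker the mean Firth interaction falls to 0.55 at a 5% rate and 0.59 at 95%, against 0.693; with a skewed biomarker it is 0.43 at 5%, 0.51 at 90% and 0.41 at 95%. Firth also does not make the interaction precise, and the report should say so. A separation check with an exact fallback, or a minimum event count, would also close the gap, but would not reduce bias and variance when estimates are finite.

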#### **Patient Selection Criteria:**

##### Inclusion Criteria:

*Patients can be enrolled into this study if all of the following criteria are met at screening visit:*

1. Hospitalized patient with clinical diagnosis of SARS-CoV-2 virus infection per World Health Organization criteria including positive nucleic acid test of any specimen (e.g., respiratory, blood, or other bodily fluid) within 2 weeks prior to screening.
2. Symptoms suggestive of severe systemic illness with COVID-19, which could include any of the following symptoms: fever, cough, sore throat, malaise, headache, muscle pain, gastrointestinal symptoms, or shortness of breath at rest, or respiratory distress.
3. Clinical signs indicative of severe systemic illness with COVID-19, which could include any of the following clinical signs: respiratory rate  $\geq$  30 per minutes, heart rate  $\geq$  125 per minute,

SpO2 ≤ 93% on room air, PaO2/FiO2 ratio < 300 mmHg, or lung infiltration >50% on chest X-ray imaging.

4. Patients with plasma CRP level >50 mg/L or 4x upper limit of normal range at screening.
5. Men or women ≥18 but ≤80 years of age at the time of signing the informed consent form.
6. Use of home oxygen is allowed
7. Patient is able to understand the purpose and risks of the study and provide signed and dated informed consent or have a legal representative provide consent and authorization to use protected health information (in accordance with national and local patient privacy regulations).
8. Patient is able to swallow tablets or receive delivery of oral suspension via a nasogastric tube.
9. Patient agrees not to participate in another interventional study after signing the informed consent form and until the end of study (EoS) visit has been completed.

Exclusion Criteria:

*Patients should be excluded from this study if any of the following criteria is met at screening visit:*

1. Patient requires endotracheal intubation and mechanical ventilation, oxygen delivered by high-flow nasal cannula (heated, humidified, oxygen delivered via reinforced nasal cannula at flow rates >20 L/min with fraction of delivered oxygen ≥ 0.5. However, periodically delivered at flow rates >20 L/min with fraction of delivered oxygen ≥ 0.5 is allowed), noninvasive positive pressure ventilation, extracorporeal membrane oxygenation (ECMO), or clinical diagnosis of respiratory failure.

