8.2 Standard Calculations

Variables requiring calculations will be derived using the following formulas:

- Baseline: A Baseline value, unless specified otherwise, is the last non-missing value recorded prior to the first dose of study drug.
- Study day: For a given date, study day will be calculated as the number of days from the day of first dosing of study drug, labeled day 1, therefore:

Study day = date of event/measurement - date of first dose of study drug + 1, for events/measurements on or after first dose

Study day = date of event/measurement - date of first dose of study drug, for events/measurements before first dose

- Durations (days): Durations, expressed in days, will be calculated as follows:

Duration in days = (Stop date/time of event – Start date/time of event)/(3660x24)

If the stop or start time is missing, only the date information will be used as follows:

Duration in days = Stop date of event – Start date of event + 1

- Height: Height entries made in inches are converted to centimeters using the following formula:

Height (cm) = Height (in) × 2.54

- Weight: Weight entries made in pounds are converted to kilograms using the following formula:

Weight (kg) = Weight (lb)/2.2046

- Body Mass Index (BMI): BMI is calculated using height and weight and is calculated using the following formula:

BMI (kg/m²) = Weight (kg) / [[Height (cm) / 100]²]

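### SAP 11.9 judges the biomarker association in each treatment group from the coefficients of an interaction model, but at most one arm's association is tested by any of those coefficients

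*SAP*

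**What the plan says.** SAP 11.9 models whether a patient had an adverse event "as a function of treatment, Baseline biomarker and the interaction between treatment and Baseline biomarker as fixed effects". The output and its use are given in one sentence: "The regression coefficients, 95% CI and corresponding P-values will be reported and used to assess the association between the following Baseline biomarker parameters" (CRP, then "Baseline Ferritin and lymphocyte counts") and "the proportion of TEAE and SAE per treatment group". Tables 14.3.11.1 and 14.3.11.2 in SAP Appendix 5 are the planned outputs, one for TEAEs and one for SAEs.

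Section 11.9 names no reference level or coding for treatment, no arm-specific slope or contrast, and no centring or scale for the biomarker. The protocol (8.2, and 10.3.2 under the correlation of biomarker profiles with safety outcome) leaves the details to the SAP, so this is where they have to appear. Elsewhere the SAP does define what is estimated: least-squares mean comparisons in 13.1.1 and 13.3, and log scale with a geometric mean ratio in 14.1.1.

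**The concern.** The question is about association within each arm. The stated evidence is a set of coefficients, and in an interaction model these answer other questions: the slope in one arm or the average slope, and the difference between slopes. Which of these the biomarker line shows depends on a programming choice that the SAP does not record. SAP 8 calls any P-value below 0.05 statistically significant, so a reader of the table could conclude that there is or is not an association in an arm that the P-value never tested.

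There is a smaller, related point. If the biomarker is not centred, the treatment coefficient in the same table is the log odds ratio at a biomarker value of zero. For CRP that lies outside the range set at entry: "Patients with plasma CRP level >50 mg/L or 4x upper limit of normal range at screening".

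**Working it through.** **Inputs from the documents.** Model terms and use of coefficients: SAP 11.9. Two-sided 0.05: SAP 8. About 30 per group, 1:1: SAP 6 and 7. The plan has no figure to reproduce: 11.9 gives no event rate or effect size, and SAP 6 says that the sample size was not calculated.

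**Assumed for illustration.** CRP lognormal with median 110 mg/L and log-SD 0.5, keeping values above 50 mg/L; event probability 50% at CRP 120 mg/L; slopes of 0, 0.6 or 1.2 logits per 50 mg/L.

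**Algebra (needs no assumption).** Write logit P = b0 + b1·T + b2·X + b3·T·X.

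- Placebo as reference (T = 1 on active): placebo slope = b2, active slope = b2 + b3. Only the placebo slope is a coefficient.
- Active as reference: the biomarker coefficient is the active slope, and the placebo slope is then no coefficient.
- Effect coding (T = −1, +1): the biomarker coefficient is the average of the two slopes and belongs to neither arm.
- Under every coding, the interaction P-value tests equality of slopes.

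**One simulated data set, 30 per arm, true slope in the active arm only.** The fit is the same each time (log-likelihood −31.92); only the coding changes.

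| Coding | Biomarker coefficient | P | What it is |
|---|---|---|---|
| Placebo reference | 0.280 | 0.490 | placebo slope |
| Active reference | 2.206 | 0.013 | active slope |
| Effect coding | 1.243 | 0.011 | average slope |

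Check: 0.280 + 1.926 (interaction, P = 0.049) = 2.206, and (0.280 + 2.206)/2 = 1.243.

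The two arm results that the SAP asks about are, as odds ratios per 50 mg/L:

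- Placebo: exp(0.280) = 1.32. With SE 0.405, the 95% CI is exp(0.280 ± 1.96 × 0.405) = 0.60 to 2.93.
- Active: exp(2.206) = 9.08, with 95% CI exp(0.464) to exp(3.948) = 1.59 to 51.8.

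**Repeated simulation, about 3,000 trials per row, percentage with P < 0.05.**

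| True slopes | Biomarker, placebo reference | Biomarker, effect coding | Interaction | Active slope (b2 + b3) |
|---|---|---|---|---|
| None | 2.6 | 4.3 | 4.9 | 2.7 |
| 1.2, active only | 2.9 | 52.7 | 52.2 | 75.2 |
| 1.2, placebo only | 73.5 | 51.8 | 50.8 | 2.3 |
| 0.6, both arms | 28.5 | 66.1 | 2.9 | 28.5 |

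In row 2 the active-arm association is found in 75.2% of trials by the right contrast, but the placebo-reference biomarker line shows it in 2.9%. In row 3 the effect-coded line is significant in 51.8% of trials although the active arm has no association.

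**Treatment coefficient.** The log odds ratio at biomarker value X is b1 + b3·X. In the data set above it is −5.779 (P = 0.027) at CRP 0 and −0.593 (SE 0.658, P = 0.367) at the sample mean. That mean is (5.779 − 0.593)/1.926 = 2.69 units of 50 mg/L, about 135 mg/L. In row 2, where the arms are equal at CRP 120 mg/L, the treatment coefficient has P < 0.05 in 47.3% of trials at CRP 0 and in 7.6% at the sample mean. On a log scale the zero point would be CRP 1 mg/L, still below the entry limit.

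**The case against.** Several stronger readings are tempting, and the documents do not support them.

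- *No coefficient tests the active-arm association.* This fails if the active arm is the reference; then placebo is the arm left untested. The SAP does not say which applies.
- *A real drug effect on SAEs would be missed because the treatment coefficient is taken at CRP zero.* Section 11.9 uses the coefficients for the biomarker association and does not present the treatment coefficient as the drug effect. The arms are compared in SAP 11.2, with a 95% CI and the Fisher exact test. What remains is a risk that a reported P-value is misread.
- *The interaction rejection rates are errors.* With equal slopes, few rejections are correct; with unequal slopes, rejections are power. They mislead only if read as a test within one arm.
- *Zero is outside the enrolled range for every biomarker.* Eligibility sets a limit for CRP only, not for ferritin or lymphocytes. Even for CRP the limit applies at screening, whereas the SAP baseline "is the last non-missing value recorded prior to the first dose of study drug".

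It can also be said that SAP 11.9 attaches the words on treatment group to the proportions, so a single overall association might be meant. The reference-coded biomarker coefficient does not give that either, so the coding would still have to be stated.

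Finally, both arm slopes can be computed later from the same fit, the study is exploratory and unpowered, and the simulated rates rest on assumed inputs. All of that is true. It limits the consequence, but the planned table still does not answer the planned question.

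**Conclusion.** The point holds in limited form. As written, SAP 11.9 produces a test of association for at most one arm, and for neither under effect coding; nothing elsewhere in the documents adds the missing contrast. This is more than absent detail, because the stated output does not answer the stated question and its biomarker P-value changes with an unstated coding choice. That conclusion is algebraic. The percentages depend on the assumed CRP distribution, event rate and slopes, and serve only as illustration.

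The consequence is modest. The analysis is listed among the secondary safety measures and is exploratory, nothing is irrecoverably lost, and the primary TEAE proportion and its comparison are untouched. The treatment-coefficient point is a precaution, documented for CRP only.

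**What to change.** Amend SAP 11.9, before unblinding, to say that:

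1. The coding of treatment is stated.
2. For each biomarker and for TEAE and SAE separately, the biomarker odds ratio with 95% CI and P-value is reported in each arm, by ESTIMATE or CONTRAST statements or by a parameterisation with the biomarker nested in treatment.
3. The interaction P-value is used only to judge whether the association differs between arms.
4. The biomarker is centred at its pooled baseline mean and its scale is stated, so that the reported treatment coefficient refers to the mean biomarker level.

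The shells for Tables 14.3.11.1 and 14.3.11.2 should follow. A log scale, odds ratios per SD and Firth estimation are optional and are not needed to cure this defect. The cost is a few lines of text and code: the model is the same, and no data or patients are added.
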